6.4.2 Peak thrombin

Peak thrombin values collected within 48 hours of factor, BPA or antifibrinolytic administration will be excluded from all analysis. Peak thrombin values will be summarized descriptively. In addition, MMRM analyses will be performed on change from baseline in peak thrombin with fixed effects of treatment arm, randomization strata of number of bleeding episodes in the

6 months prior to study entry (≤ 10 vs > 10), randomization strata of hemophilia type (A vs B), visit and baseline peak thrombin level. The covariance structure will be chosen to minimize BIC.

Both analyses in AT and peak thrombin may also be performed on a logarithmic scale. The estimates along with 90% confidence intervals will be back transformed to the original scale.

6.4.3 AT Lowering and peak thrombin

Correlation between AT (actual AT levels and AT lowering) and thrombin will be computed on paired assessments, where both parameters are measured on the same day. Log transformation may be used.

6.5 Pharmacokinetic analysis

Non-compartmental analysis for PK parameter estimation in East Asian patients from East Asian sites is described in this analysis plan. Population PK analysis is planned for all patients in the study and will be described in a separate population PK analysis plan.

Pharmacokinetic parameters to be estimated using noncompartmental analysis will include, but will not be limited to: maximum plasma concentration (C_{max}), time to maximum plasma concentration (t_{max}), elimination half-life ($t_{1/2\beta}$), area under the concentration-time curve (AUC), apparent clearance (CL/F), and apparent volume of distribution (V/F). Other parameters may be calculated, if deemed necessary. PK analysis is not in the scope of this SAP and will be reported separately.

6.6 Safety analyses

Safety analyses will be conducted using the Safety Analysis Set. All safety summaries will be presented by treatment arm and may include the overall column as specified.

6.6.1 Study duration, study drug exposure and compliance

Study duration in treatment period in days is calculated as EOS/ET visit date – Day 1 visit date (or date of first dose of study drug for fitusiran arm) +1. Total study duration including AT follow-up in days is calculated as date of last follow-up – Day 1 visit date (or date of first dose of study drug for fitusiran arm) +1. The number of patients in each 2 month interval and summary statistics for the study duration by treatment group will be presented.

Exposure to study medication in days and the total number of study drug SC administrations received will be summarized for Fitusiran arm.

Duration of treatment exposure in days is calculated as date of the last dose of study drug – the date of the first dose of study drug + 28. The number 28 is the number of days between two scheduled doses of study drug. For example, if the last dose of study drug is taken on Day 31, the treatment exposure would be calculated as $(31-1) + 28 = 58$ days.

Dose interruptions and compliance are not taken into account for duration of exposure.

Fitusiran treatment compliance will be calculated as the total mg dose received as the percentage of total mg dose expected to receive. Fitusiran treatment compliance will be summarized.

6.6.2 Adverse events

All AEs will be coded using the MedDRA coding system (version used at the time of the database lock) and displayed in tables and data listings using system organ class (SOC) and preferred term (PT).

Analyses of AEs will be performed for those events that are considered treatment-emergent, and will be referred to as TEAEs. Treatment emergent AE is defined as any AE with onset date after first fitusiran dose for fitusiran arm or after Day 1 visit for the on-demand arm. Events with a fully or partially missing onset date will be assumed to be treatment emergent unless it can be unequivocally determined (from the partial onset date and/or a partial or complete stop date) that the event occurred prior to the first dose for fitusiran arm or prior to Day 1 visit for the on demand arm.

AEs will be summarized by the numbers and percentages of patients reporting at least one AE, having at least one AE by primary System Organ Class (SOC) and Preferred Term (PT). A patient with multiple occurrences of an AE will be counted only once in the respective AE category. Patients who report multiple occurrences of the same AE (preferred term) will be classified according to the most related or most severe occurrence, respectively.

All AE summaries will be presented (frequency counts and percentages) by system organ class and/or preferred term, unless specified otherwise. The SOC will be presented alphabetically and the preferred term will be sorted within each SOC in decreasing order of frequency in the fitusiran arm.

The following events are considered to be AEs of special interest (AESI):

- ALT or AST elevations $>3 \times$ ULN
- Suspected or confirmed thromboembolic events
- Severe or serious injection site reactions (ISRs), ISRs that are associated with a recall phenomenon (reaction at the site of a prior injection with subsequent injections) or, those that lead to temporary dose interruption or permanent discontinuation of study drug.
- Systemic injection associated reactions (IARs), defined as hypersensitivity reactions which are related or possibly related to study drug.

An overall summary of AEs will include the number and percentage of patients with any AE, any AE assessed by the Investigator as related to study drug (fitusiran only, possibly related or definitely related), any severe AE, any severe AE related to study drug, any serious AE (SAE), any SAE related to study drug, any AE/SAE of special interest; any AE/SAE leading to study drug discontinuation, any study drug related AE/SAE leading to study drug discontinuation, any AE/SAE leading to study withdrawal, any study drug related AE/SAE leading to study

withdrawal, AE potentially consistent with COVID-19 and any deaths. The overall summary of AEs will also be provided by hemophilia type.

Tabulations by SOC and PT will be produced for the following:

- all AEs;
- AEs by severity;
- AEs by hemophilia type
- all SAEs;
- AEs related to study drug (fitusiran arm only);
- AEs related to study drug by hemophilia type (fitusiran arm only);
- SAEs related to study drug (fitusiran arm only);
- SAEs related to study drug by hemophilia type (fitusiran arm only);
- AESI;
- AESI by hemophilia type;
- SAEs of special interest;
- SAEs of special interest by hemophilia type;
- AEs leading to study drug discontinuation (fitusiran arm only);
- SAEs leading to study drug discontinuation (fitusiran arm only);
- AESIs leading to study drug discontinuation (fitusiran arm only);
- Serious AESIs leading to study drug discontinuation (fitusiran arm only);
- AEs leading to study withdrawal;
- SAEs leading to study withdrawal.
- AEs potentially consistent with COVID-19;

COVID-19 infection will be identified based on the search term list in Appendix 8.2.

Tabulations by PT in decreasing order in frequency in the fitusiran arm will be produced for the following:

- all AEs;
- all AEs by hemophilia type;
- all SAEs;
- AEs related to study drug (fitusiran arm only);
- SAEs related to study drug (fitusiran arm only);

All AEs collected will be listed along with the information collected on those AEs, eg, AE relationship to study drug, AE outcome etc. AEs that are not treatment-emergent will be flagged in the listings. By-patient listings will also be provided for the following: all patient deaths, all

SAEs, and all AEs leading to study drug discontinuation or study withdrawal, all AEs leading to death, AEs potentially consistent with COVID-19.

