^r Blood samples for PK analysis will be collected at the timepoints listed in Table 7 in all fitusiran arm patients. In East Asian patients in the fitusiran arm at East Asian sites, blood samples for PK analysis will be collected at the time points listed in Table 8 (which includes those time points listed in Table 7), and pooled urine for PK analysis will be collected at the time points listed in Table 9.

^s Must be completed at the clinic. Will be collected at EOS visit, not be collected at ET visit.

^t Will include review of entries, (symptoms of bleed events, bleed causality, bleed severity, doses administered), whether appropriate site contact occurred regarding treatment of bleeds, and review of patient bleed management plan and recommendations and requirements for site contact regarding dosing.

^u It is preferred that factor concentrate administration and bleeding events are entered in the eDiary immediately or within 24 hours. Additional patient follow-up may be required as described in Section 7.2.1. Patients in the fitusiran treatment arm who present in the clinic with symptoms characteristic of a potential bleeding episode should have assessments completed per Table 2.

^v Perioperative assessment of safety and hemostatic efficacy only in patients undergoing operative procedures while on study (see Table 10).

^w AEs will be monitored and recorded from date of signed informed consent through Follow-Up. Signs and symptoms of thrombosis will be evaluated at every visit (see Section 6.5).

^x In addition to recording concomitant medications, documented history of prior medications will be collected during Screening.

Table 2: Bleeding Episode Assessments – Unscheduled Visit

| | Predose | Postdose 10 min (± 5 min) ^d | Postdose 60 min (± 5 min) ^d |
|--|---------|--|--|
| Directed Physical Examination ^a | X | | |
| Vital Signs | X | | |
| AT | X | | |
| FVIII/IX Levels | X | X | X |
| TG | X | X | X |
| Coagulation | X | X | X |
| Hematology | X | X | X |
| Exploratory Coagulation ^b | X | | X |
| Optional Imaging ^c | X | | |

Abbreviations: AT=antithrombin; BPAs=bypassing agents; FVIII=factor VIII; FIX=factor IX; TG=thrombin generation

^a See Section 7.5.3 for assessments to be performed during a directed physical examination.

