| Mild: | Mild; asymptomatic or mild symptoms; clinical or diagnostic observations only; intervention not indicated |
| Moderate: | Moderate; minimal, local, or noninvasive intervention indicated; limiting age appropriate instrumental activities of daily living (eg, preparing meals, shopping for groceries or clothes, using the telephone, managing money) |
| Severe: | Severe or medically significant but not immediately life-threatening; hospitalization or prolongation of hospitalization indicated; disabling; limiting self-care activities of daily living (ie, bathing, dressing and undressing, feeding self, using the toilet, taking medications, and not bedridden); OR life-threatening consequences; urgent intervention indicated; OR death related to an AE |

Changes in severity should be documented in the medical record to allow assessment of the duration of the event at each level of severity. Adverse events characterized as intermittent require documentation of the start and stop of each incidence. When changes in the severity of an AE occur more frequently than once a day, the maximum severity for the experience that day should be noted. If the severity category changes over a number of days, then those changes should be recorded separately (with distinct onset dates).

Adverse event severity and seriousness are assessed independently. ‘Severity’ characterizes the intensity of an AE. ‘Serious’ is a regulatory definition and serves as a guide to the Sponsor for defining regulatory reporting obligations (see definition for SAE).

Relationship of the Adverse Event to Study Treatment

The relationship of each AE to study treatment should be evaluated by the Investigator using the following criteria:

| | |
|---------------------|---|
| Definitely related: | A clinical event, including laboratory test abnormality, occurring in a plausible time relationship to the medication administration, and which cannot be explained by concurrent disease or other drugs or chemicals. The response to withdrawal of the drug should be clinically plausible. |
| Possibly related: | A clinical event, including laboratory test abnormality, with a reasonable time sequence to the medication administration, but which could also be explained by concurrent disease or other drugs or chemicals. Information on the drug withdrawal may be lacking or unclear. |

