7.5.6.2. Eliciting and Recording Adverse Events

Eliciting Adverse Events

The patient should be asked about medically relevant changes in his health since the last visit, with attention to any signs and symptoms that could be consistent with thrombosis. The patient should also be asked if he has been hospitalized, had any accidents, used any new medications, or changed concomitant medication routines (both prescription and OTC). In addition to patient observations, AEs will be documented from any clinically relevant laboratory findings, physical examination findings, ECG changes, or other findings that are relevant to patient safety.

Recording Adverse Events

The Investigator is responsible for recording non-serious AEs and SAEs that are observed or reported by the patient after the time when the informed consent is signed regardless of their relationship to IMP through the end of study. Non-serious AEs will be followed until the end of study. SAEs will be followed until satisfactory resolution, until baseline level is reached, or until the SAE is considered by the Investigator to be chronic or the patient is stable, as appropriate.

All AEs must be recorded in the source records for the clinical study center and in the eCRF for the patient, whether or not they are considered to be drug-related. Each AE must be described in detail: onset time and date, description of event, severity, relationship to investigational drug, action taken, and outcome (including time and date of resolution, if applicable).

For SAEs, record the event(s) on both the eCRF and the SAE form.

For AEs that are considered AESI (Section 7.5.6.1), the Sponsor or its designee should be notified within 24 hours using a supplemental AESI eCRF. Additional clinical and laboratory information may be collected; see Section 6.2.3.1 regarding monitoring for liver abnormalities.

Refer to eCRF completion guidelines for details on reporting events in the supplemental AESI eCRF.

Since bleeding episodes are recorded as an efficacy assessment of fitusiran, these will not be treated as AEs unless they meet any of the SAE criteria listed in Section 7.5.6.1. The manifestation and frequency of bleeding episodes is an efficacy indicator of this study and ABR is the focus of the primary and secondary efficacy analyses.

Recording an ISR

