8.2.8. Safety Analyses

Extent of exposure will be summarized. Safety will be based on all AEs having onset (start or worsening in severity) within the study and on the Safety Analysis Set. Incidence of AEs, AEs by maximum severity, AEs by relationship to study medication, SAEs and AEs leading to discontinuation of treatment will be presented.

Descriptive statistics will be provided for clinical laboratory data, ECG and vital signs. Laboratory shift tables from baseline to worst post-baseline values may be presented.

Other safety summaries will be presented as appropriate. Further details will be specified in the SAP.

Adverse events will be classified according to the MedDRA System Organ Class and Preferred Term. Prior and concomitant medications will be classified according to the World Health Organization (WHO) drug dictionary.

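### The SAP identifies treatment-emergent AEs by onset date alone, without the protocol's worsening criterion, so AEs already present before treatment can be misclassified in either direction depending on how severity changes are recorded

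*SAP*

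**What the plan says.** Protocol 8.2.8 (Safety Analyses) sets the basis for safety reporting: "Safety will be based on all AEs having onset (start or worsening in severity) within the study and on the Safety Analysis Set". Onset there has two limbs, a start or a worsening.

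SAP 6.6.2 (Adverse events) keeps only a date test. It states "Analyses of AEs will be performed for those events that are considered treatment-emergent, and will be referred to as TEAEs", and then: "Treatment emergent AE is defined as any AE with onset date after first fitusiran dose for fitusiran arm or after Day 1 visit" (the latter in on-demand patients). It does not mention worsening, severity before treatment, or several records belonging to one event.

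Two protocol rules on recording bear on how that date test works:

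- Table 1, footnote w: "AEs will be monitored and recorded from date of signed informed consent through Follow-Up". Screening runs from Day -60 to Day -1, so AEs can be on file before treatment begins.
- Section 7.5.6.1, under AE severity: "If the severity category changes over a number of days, then those changes should be recorded separately (with distinct onset dates". The rule does not depend on the direction of the change. Where severity changes more than once within a day, only that day's maximum is noted.

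SAP 2.5 and 2.6 tabulate major changes. The AE entries there concern AEs of special interest, COVID-19 and summaries by hemophilia type. Neither table mentions the worsening criterion.

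**The concern.** A date test identifies emergent events correctly only if each onset date marks a start or a deterioration. The protocol's recording rule also creates an onset date when an AE improves. The SAP definition cannot tell such a date from a true onset, because it never looks at what the severity was before treatment.

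The protocol's safety endpoint is the incidence, severity, seriousness and relatedness of AEs, and the SAP's AE summaries are built on the TEAE flag. If the flag is wrong for a patient, the patient is wrongly counted in, or left out of, the incidence tables for that preferred term, its system organ class and the overall AE row. The outcome also depends on how sites or the eCRF handle severity changes, which the analysis plan should not leave open.

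**Working it through.** The plan gives no figure to reproduce. The check is to trace AE histories through the two rules.

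**Inputs.** The anchor is the first fitusiran dose or, for on-demand, the Day 1 visit (SAP 6.6.2). Severity is mild, moderate or severe (protocol 7.5.6.1). AE collection starts at consent (protocol Table 1 footnote w and 7.5.6.2). Planned arm sizes are 80 and 40 (protocol 1.3). About 26 patients are to have hemophilia B (protocol 4.3), randomized 2:1 within hemophilia type (protocol 4.4).

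**Cases.** The study days are illustrative, with the anchor at Day 1. The second column applies the protocol's start-or-worsening idea after the anchor.

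| AE history | Starts or worsens after anchor? | SAP rule, records split | SAP rule, one record |
|---|---|---|---|
| (a) Severe from Day -10, mild from Day 5 | No | TEAE (mild), from the Day 5 record | Not a TEAE |
| (b) Mild from Day -10, severe from Day 5 | Yes | TEAE (severe), from the Day 5 record | Not a TEAE |
| (c) New on Day 20, eases on Day 25 | Yes | TEAE, patient counted once | TEAE, patient counted once |
| (d) From Day -10, severity unchanged | No | Not a TEAE | Not a TEAE |

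With split records the SAP rule fails in (a) and is right in (b). With a single record it is right in (a) and fails in (b). Neither practice makes the rule right in all four cases.

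**Do other SAP rules repair this?**

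- Counting each patient once per AE category removes duplicates, but leaves a lone improvement record in place.
- Taking the most severe or most related occurrence only chooses among records.
- The listing flag for AEs that are not treatment-emergent uses the same definition.
- Nothing in SAP 6.6.2 links the records of one event.

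**Scale.** With k misclassified patients in an arm, the incidence shifts by k/N. For k = 1:

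- Fitusiran: 1/80 = 0.0125, or 1.25 percentage points.
- On-demand: 1/40 = 0.025, or 2.5 percentage points.
- Hemophilia B tables (SAP 6.6.2 tabulates AEs by hemophilia type): 26 × 2/3 ≈ 17 on fitusiran and 26 × 1/3 ≈ 9 on on-demand. One patient is then 1/17 ≈ 5.9 points or 1/9 ≈ 11.1 points.

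The documents do not give k. In case (a) it counts only patients whose AE began between consent and the anchor, was still ongoing, then fell by a severity category, and who had no other TEAE in the same category. In case (b) it counts only those whose AE worsened without a new record and who had no other TEAE in that category.

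**The case against.** The other side has five fair points.

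- **The protocol sentence has no first-dose cut-off.** It says "Safety will be based on all AEs having onset (start or worsening in severity) within the study", and AEs are recorded from consent. A reader might infer that the SAP counts a patient whom the protocol excludes. The text does not support that: an AE that starts in screening may already fall within the protocol's sentence. What stands is narrower. The SAP introduces a treatment-emergent cut-off and then applies it without the worsening criterion, so an improvement can be labelled treatment-emergent.
- **The SAP says AE, not AE record.** Protocol 7.5.6.1 explains severity tracking as a way to measure time at each severity level, which reads like one event in segments. The eCRF design and completion guidelines are not available to us. This stands, and it is why the over-count is conditional on split records reaching the analysis data.
- **The two errors need opposite recording practice.** A reader might infer that over-counting and missed worsening occur together. For any one event they cannot, and the missed worsening requires the separate-entry rule not to be carried through. This limits the harm, but it also shows that the definition is not robust to either practice.
- **Not every table is touched.** Drug-related tables are for the fitusiran arm only, and an AE that predates dosing is unlikely to be attributed to the drug. Injection-site and injection-associated reactions cannot precede an injection. Entry criteria exclude ALT or AST above 1.5 times the upper limit of normal, so a pre-dose elevation of special interest is improbable. Bleeds are not AEs unless serious. A claim that all TEAE tables are inflated would go too far.
- **No between-arm comparison is at stake.** Safety is summarized descriptively. A reader might infer dilution of a fitusiran-to-on-demand ratio, but no such ratio is planned, and any size for it would rest on invented incidences.

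The listings also keep the pre-dose record visible. That helps someone reading listings but does not correct the tables.

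**Conclusion.** The point holds in conditional form. The SAP's TEAE rule leaves out the protocol's worsening criterion, and its tables of changes do not say so. Read with the protocol's own recording rule, it lets an AE from before treatment that only improves count as treatment-emergent. If severity changes are not split, it omits a true worsening instead.

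The affected number is probably small and cannot be derived from the documents. The sizes of 1.25 and 2.5 points per patient assume the planned 80 and 40 as denominators and no other TEAE in the same category. The hemophilia B figures further assume that about 26 such patients are enrolled and split 2:1.

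This is worth correcting because a stated rule can give wrong counts, not merely because detail is missing. It does not threaten the efficacy conclusions or any planned test.

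**What to change.** In SAP 6.6.2, replace the definition with one that says:

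1. A TEAE is an AE that newly starts after the first fitusiran dose (Day 1 visit for on-demand), or an AE present before that point whose severity afterwards exceeds its worst severity before it.
2. Severity records belonging to the same event are linked before the flag is derived. The SAP should name the linking rule, for example an event identifier if the eCRF has one, otherwise the same preferred term with contiguous dates.
3. A linked record that continues a pre-dose or pre-Day 1 AE at equal or lower severity is not treatment-emergent.

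Add a line to the change table in SAP 2.6.

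The cost is SAP wording and one derivation flag, set before database lock. The protocol already requires the inputs: "Each AE must be described in detail: onset time and date, description of event, severity, relationship to investigational drug, action taken, and outcome". If the eCRF holds a single onset date per event with severity overwritten, the separately recorded severity changes would have to be retrieved from source, so the eCRF layout should be checked first. Patient care and the visit schedule do not change.

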4.2. Duration of Treatment

The duration of treatment with fitusiran is 9 months. The estimated total time on study, inclusive of Screening, for each patient is up to 11 months for all patients who enroll in the extension study and patients in the on-demand arm who do not enroll in the extension study. The estimated total time on study may be up to 17 months in fitusiran treatment arm patients who do not enroll in the extension study due to the requirement for an additional 6 months of follow-up for monitoring of AT levels.

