9.1.4. End of the Study

The end of the study is defined as the last patient last visit.

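### The treatment-emergent AE window has no end, so the by-arm AE, AESI and liver percentages cover longer observation for fitusiran patients who stay out of the extension

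*SAP*

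**What the plan says.** **Definition.** SAP 6.6.2 counts as treatment-emergent "any AE with onset date after first fitusiran dose for fitusiran arm or after Day 1 visit for the on-demand arm". This fixes a start. Neither that section nor any other part of the SAP fixes an end. Protocol 8.2.8 sets no upper limit either: "Safety will be based on all AEs having onset (start or worsening in severity) within the study".

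**Collection.** Protocol Table 1, footnote w: "AEs will be monitored and recorded from date of signed informed consent through Follow-Up". Protocol 7.5.6.2 has AEs recorded "regardless of their relationship to IMP through the end of study", and 9.1.4 adds: "The end of the study is defined as the last patient last visit".

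**Who is followed.** Table 1, footnote c, limits the AT follow-up visits to fitusiran patients who do not enter the extension. Protocol 4.2 puts total time on study at "up to 11 months for all patients who enroll in the extension study and patients in the on-demand arm who do not enroll", but says it "may be up to 17 months in fitusiran treatment arm patients who do not enroll in the extension study", the reason being "an additional 6 months of follow-up for monitoring of AT levels".

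**Summaries.** SAP 6.6 and 6.6.2 present AEs, SAEs and AESIs as numbers and percentages of patients by arm. SAP 6.6.3 counts patients in ALT, AST and bilirubin categories over all post-baseline time. No exposure-adjusted rate is planned, and no table separates the follow-up period. SAP 6.6.1 does define two durations, one for the treatment period and one that includes AT follow-up, but the AE section uses neither.

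**The concern.** A crude percentage of patients with an event rises with time observed. If part of one arm is watched for longer, its percentages tend to be higher even when the underlying risk is the same.

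Two features add to this:

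- **More testing in one arm.** Table 1 schedules liver function tests at the AT follow-up visit. Those fitusiran patients get further chances to meet the ALT/AST AESI criterion after on-demand patients have left.
- **Mixed conditions.** Under Protocol 6.3.1.3, patients who stop fitusiran may return to standard factor dosing as AT recovers. Events under those conditions would be pooled with on-treatment events under one label, and thrombosis is among the AESIs.

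The SAP recognises the issue for efficacy. Section 6.3 drops bleeding data from 28 days after fitusiran discontinuation. It makes no corresponding split for safety.

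**Working it through.** **1. The plan's own figures.** Table 1 gives up to 60 days of screening and an EOS/ET visit on Day 253.

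- 60 + 253 = 313 days; 313/28 = 11.2 four-week months (10.3 calendar months). The protocol states up to 11.
- Adding six 28-day months: (313 + 168)/28 = 17.2. The protocol states up to 17.
- Difference: 17 − 11 = 6 months.

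The stated durations reproduce.

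**2. Observation window per patient.** On-demand patients and extension enrollees: 253 days. A fitusiran patient with the full extra six months:

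- 253 + 168 = 421 days, ratio 421/253 = 1.66 (28-day months)
- 253 + 183 = 436 days, ratio 436/253 = 1.72 (calendar months)

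**3. Effect on crude percentages with no true difference between arms.** Assumptions, none of them given in the documents:

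- one constant hazard, the same in both arms and before and after the last dose;
- a share q of fitusiran patients outside the extension, each with the full 183 extra days.

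With p the incidence by Day 253:

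- hazard h = −ln(1 − p)/253
- fitusiran percentage = (1 − q)·p + q·[1 − exp(−436h)]

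For p = 10%, 1 − 0.9^(436/253) = 16.6%. For p = 30%, 1 − 0.7^(436/253) = 45.9%.

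| q | p = 10% shows as | ratio | p = 30% shows as | ratio |
|---|---|---|---|---|
| 10% | 0.9×10 + 0.1×16.6 = 10.7% | 1.07 | 31.6% | 1.05 |
| 20% | 0.8×10 + 0.2×16.6 = 11.3% | 1.13 | 33.2% | 1.11 |
| 50% | 0.5×10 + 0.5×16.6 = 13.3% | 1.33 | 38.0% | 1.27 |

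**4. Shorter follow-up.** With three 28-day months (84 extra days), 1 − 0.9^(337/253) = 13.1%. A 10% event then shows as 10.3%, 10.6% or 11.5% for q = 10%, 20% or 50%.

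**5. In patients.** Protocol 1.3 plans 80 patients on fitusiran. For a 10% event with the full six months, the excess is about 0.7% × 80 = 0.5 patient at q = 10% and 3.3% × 80 = 2.6 patients at q = 50%.

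**The case against.** **The figures are near a ceiling.** This stands. Six months is a maximum, since follow-up ends once AT activity is back to about 60% or at the investigator's discretion. AT visits run from the final dose, so a patient last dosed on Day 57 with six months of visits finishes near Day 57 + 183 = 240, inside the 253 days, yet the formula gives him 436. Even a patient last dosed on Day 225 would finish near Day 408 on that count, 155 extra days rather than 183. The hazard after the last dose may also differ from the hazard on treatment.

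**Safety is descriptive.** This stands in part. No between-arm safety test or risk ratio is planned, so the ratios above are not outputs of the trial. Readers will still compare the two columns.

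**The open window follows the protocol and is cautious.** This stands as a reason to keep the all-study tables. Protocol 8.2.8 takes in all AEs within the study, and EOS is only 253 − 225 = 28 days after the last scheduled dose. A hard cut there would take later thrombotic or liver events out of the main tables while AT may still be lowered. It does not justify having no like-for-like table.

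**The imbalance will be visible.** Partly. SAP 6.6.1 reports both durations by arm and all AEs are listed. Neither adjusts the percentages.

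**Collection might stop at Month 9.** If end of study in Protocol 7.5.6.2 is read as the EOS visit, that section conflicts with footnote w. The definition in 9.1.4 points the other way, and the SAP would still need to state the window.

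**Conclusion.** The gap is real. Followed as written, the plan produces by-arm AE, AESI and liver percentages over unequal observation time, and the tendency is to inflate fitusiran incidence. Its size cannot be fixed from the documents. For a 10% event, the range runs from 10.3% (10% outside the extension, three months of follow-up) to 13.3% (50% outside, full six months), under equal constant hazards. With high rollover it amounts to a fraction of a patient.

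A reader might infer two stronger things that the documents do not support:

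- **That the safety comparison is distorted by a known and large amount.** The share outside the extension has no source, six months is a limit rather than an expectation, and an equal post-dose hazard is only an assumption.
- **That AEs after Month 9 should not be collected, or should leave the main tables.** Collecting them while AT recovers is appropriate and within the protocol's stated safety scope. What is missing is an analysis that puts both arms on the same footing.

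The efficacy analyses are not affected.

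**What to change.** Keep the all-study treatment-emergent tables, as Protocol 8.2.8 implies, and add to SAP 6.6.2 and 6.6.3:

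1. Between-arm AE, AESI and liver tables restricted to first dose (fitusiran) or Day 1 (on-demand) through the Month 9 EOS/ET visit in both arms.
2. A separate fitusiran table of AEs with onset during AT follow-up.
3. Exposure-adjusted rates per patient-year, using the SAP 6.6.1 treatment-period duration for the restricted tables and the total duration for the all-study tables, so that numerator and denominator cover the same time. These rates also deal with unequal early termination, which the EOS/ET cut-off alone does not.

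The SAP should also say explicitly that AE recording runs through AT follow-up, so that Protocol 7.5.6.2 and footnote w are read the same way.

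The cost is a few sentences and a few extra tables, with no new data. The downside is that the restricted tables omit late events. They should refer the reader to the follow-up and all-study tables, so that thrombotic or liver events after the last dose are not overlooked.
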